Title: A Comparative Study on Effects of Defect Closure Versus Non-Closure in Laparoscopic Totally Extraperitoneal Repair of Direct Inguinal Hernia

Running Title: Study on Effects of Defect Closure in Laparoscopic TEP Repair of Direct Inguinal Hernia

AIMS AND OBJECTIVES:

Aim: To Compare the Effects of Defect Closure versus Non-Closure on Outcomes of Laparoscopic TEP Direct Inguinal Hernia Repair.

Primary Objectives

- To compare Seroma formation rate in defect closure and non-closure groups.
- To compare the score of pain in VAS on different interval of time in both groups.

Secondary objectives

- To evaluate the operative time and the length of post-operative hospital stays in both groups.
- To evaluate the complication rate: vessel / visceral injury / vas injury/ peritoneal tear.
- Days to resume normal activities and work.

RESEARCH HYPOTHESES

Null Hypothesis: There is no difference between defect closure and non-closure of Laparoscopic TEP direct Inguinal hernia repair.

Alternate Hypothesis: Defect closure is superior to non-closure in laparoscopic direct inguinal hernia repair.

Review of Literature

Materials and Methods:

- a) Type of study design: A prospective cohort study reported as the CONSORT guideline.
- b) **Study Population**: Patients attending the outpatient department of surgery with complain of inguinal hernia

c) Population/Participants:

Inclusion criteria

- 1. Age greater than 18 years
- 2. uncomplicated direct inguinal hernia (≥M3)

Exclusion criteria

- 1. Defect size ≤M2
- 2. Complicated hernia (irreducible, obstructed, or recurrent hernia)
- 3. Patient unfit for general anesthesia
- 4. Patient not giving consent
- d) **Setting**: The study was conducted at B.P. Koirala institute of Health science (BPKIHS), Dharan, an independent health university in Nepal.
- e) **Study period**: The study was conducted over a period of 12 months from September 2020 to August 2021.
- f) **Ethical clearance:** The study was performed in accordance with the principle of the declaration of Helsinki and after approved by the Institutional Review Committee and Protocol committee.

ENROLLMENT OF PATIENTS

Patients with inguinal hernia presenting to surgery OPD with the inclusion criteria of age greater than 18 years and uncomplicated direct inguinal hernia (≥M3) were enrolled in the study. A total of 88 patients were enrolled in the study using the purposive alternate number sampling

technique. They were divided into 2 groups: 44 patients each in the defect closure and non-closure groups. All patients were explained and familiarized with the visual analog score (VAS) pain chart preoperatively.

At discharge the patient will be given a chart to fill which will have daily visual assessment of pain as well as the following instructions:

- To return to normal activity as soon as possible.
- To record all analgesic intake.
- To return for follow up at 10days, 1 months, 3 months and 6 months
- To return at any time if any complication arises.
- During the follow up, assessment data will be recorded using annexure.

ANNEXURES

Proforma

Particulars of patient Serial no:					
Patient ID:					
Date:					
Name:					
Age:					
Sex: Male / Female					
Address:					
Occupation: No / Student / Business / Service/ Others					
Religion: Hindu / Buddhist / Muslim / Kirati / Christian					
Marital status: Unmarried / Married					
Socio-economic status: Low / Medium / High					
Phone no:					
History					
Examination of the patient					
1. Direct/ Indirect:					
2. Defect Size: if applicable					
3. Content: Empty/Omentum/Bowel					
4. Cough impulse: Present/Absent					
5. Reducibility: Complete/Incomplete					
ASA grading:					
Operative Procedure and Date:					
Operative Time:					
O (D ()					

Operative Detail:

1. Type of hernia:

- 2. Contents:
- 3. Type of Mesh used

Intra Operative Complications:

- 1. Injury to Visceral organs: Yes/No
- 2. Injury to vessels: Yes/No
- 3. Peritoneal tear: Yes/No
- 4. Injury to vas: Yes/No

Late complications:

- 1. Seroma formation: Yes/No
- 2. Incisional hernia/recurrence: Yes/No

FOLLOWUP

Follow up Performa (seroma formation questionnaire to be filled up by 10 days, 30 days, 3 months and 6 months)

Day 10

- 1. Seroma formation: yes / No
- 2. Pain: yes/ No
- 3. Recurrence: yes / No

1 months

- 1. Seroma formation: yes / No
- 2. Pain: yes/ No
- 3. Recurrence yes/ No

3rd month

- 1. Seroma formation: yes / No
- 2. Pain: yes / No
- 3. Recurrence yes / No

6th month

- 1. Seroma formation: yes / No
- 2. Pain: yes / No
- 3. Recurrence yes / No

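### Is the 12-month study period too short to hold the 6-month follow-up?

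*Protocol*

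**What the plan says.** Materials and Methods, item e) of the protocol gives the calendar: "The study was conducted over a period of 12 months from September 2020 to August 2021". The discharge instructions under Enrollment of patients tell each patient "To return for follow up at 10days, 1 months, 3 months and 6 months". The follow-up form in the annexures repeats the schedule, with the "seroma formation questionnaire to be filled up by 10 days, 30 days, 3 months and 6 months", and asks about seroma, pain and recurrence (yes or no) at each visit.

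Two primary objectives draw on this schedule: "To compare Seroma formation rate in defect closure and non-closure groups" and "To compare the score of pain in VAS on different interval of time in both groups". Neither names a time point. On numbers, "A total of 88 patients were enrolled in the study", with "44 patients each in the defect closure and non-closure groups".

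The protocol gives no date of first or last enrolment and no date of last follow-up. It does not say whether the 12 months are the enrolment window or the whole study.

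**The concern.** A study that lasts 12 months in all and follows each patient for 6 months can operate on patients only in its first 6 months. The protocol gives no such cut-off. A reader who takes September 2020 to August 2021 as both the enrolment window and the end of data collection will conclude that anyone operated on after February 2021 never reached a 6-month visit.

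Seroma is a primary outcome without a fixed time point, so the late visits cannot be dismissed as irrelevant to the main comparison. If visits that had not come due were recorded as negative and all 44 patients per group kept in the denominator, late seroma and recurrence rates would look lower than they were. The form offers only yes and no, with no box for a visit not made. The late results would also come only from patients treated early in the period.

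**Working it through.** **Inputs from the protocol.** Study period 12 months (item e). Visits at 10 days and 1, 3 and 6 months (discharge instructions and follow-up form). 88 patients, 44 per group (Enrollment of patients).

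**Inputs not in the protocol.** The length of the enrolment window, A months; the accrual pattern; the date on which data collection stopped. All three are assumptions below.

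**The stated figures.** 1 September 2020 to 31 August 2021 is 365 days, or 12 calendar months, as stated. 44 + 44 = 88, as stated.

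**Reading 1: the 12 months cover enrolment and follow-up.** Enrolment must close at month 12 − 6 = 6, about the end of February 2021. The pace needed is 88/6 = 14.7 patients a month. The protocol gives no accrual rate that rules this out. Visits lost: 0.

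**Reading 2: the 12 months are the enrolment window.** The last 6-month visit falls at month 12 + 6 = 18, about the end of February 2022. The pace needed is 88/12 = 7.3 a month. Visits lost: 0.

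**Reading 3: enrolment runs for A months and collection stops at month 12.** With even accrual, the share of patients whose visit at v months is not reached is max(0, A + v − 12)/A.

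| A (months) | No 6-month visit | No 3-month visit |
|---|---|---|
| 6 | 0/6 = 0% (0 of 88) | 0% (0) |
| 8 | 2/8 = 25% (22) | 0% (0) |
| 9 | 3/9 = 33% (about 29) | 0% (0) |
| 10 | 4/10 = 40% (about 35) | 1/10 = 10% (about 9) |
| 12 | 6/12 = 50% (44) | 3/12 = 25% (22) |

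At A = 12 the early visits lose little: 1/12 = 8% (about 7 patients) at 1 month and 10/365 = 3% (about 2 patients) at 10 days.

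**Sensitivity to the accrual pattern, A = 12.** If accrual rises linearly from zero, the share enrolled in the first 6 months is (6/12)² = 25%, so 75% (66 of 88) miss the 6-month visit. If it falls linearly to zero, the share enrolled in the last 6 months is (6/12)² = 25%, so 25% (22 of 88) miss it. One half is therefore the even-accrual value and not a maximum.

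**Which outcomes are exposed.** Operative time and intraoperative injury are fixed at surgery, and hospital stay soon after. Pain is also charted daily from discharge. Recurrence is on the form but is not among the listed objectives. Exposure is confined to the 3- and 6-month entries for seroma, pain and recurrence.

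**The case for a change.** The strongest case for acting is that each workable reading needs a date the protocol does not give, and that enrolment and follow-up dates belong in a protocol and not in an analysis plan. Reading 1 needs about 14.7 operations a month at one named institution, which some would doubt. Even a modest overrun of enrolment costs data: 8 months of accrual with a stop at month 12 loses a quarter of the 6-month visits. One added sentence would settle the matter.

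The missing dates are real, and that part stands. The rest does not establish a fault. Doubt about 14.7 a month has no accrual figure in the protocol behind it, and if the pace was slower, Reading 2 is available and loses nothing. Nothing in the text says that promised visits were abandoned in August 2021.

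The further harms are not in the document either. The follow-up form has a separate block for each visit, so a visit not made would naturally be left blank. Denominators and the handling of missed visits are commonly left to the statistical analysis plan, which is not at hand. No surgeon's case sequence or learning curve is described. Finally, the protocol describes an alternate-number scheme. If that means patients alternated between groups, a calendar cut-off would fall about equally on both, so the cost would be precision at the late visits and not a lean toward either group.

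**Conclusion.** No change to the plan follows. The 12-month period and the 6-month visit are compatible on both natural readings, with no visits lost on either. The loss of about 50% of 6-month visits and 25% of 3-month visits needs three assumptions together: enrolment to the end of August 2021, data collection stopping then, and even accrual. The protocol states none of them. With the first two granted, linear accrual patterns alone move the 6-month loss between 25% and 75%.

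What survives is an omission of detail: the last enrolment date and the last follow-up date are not written down. The enrolment text is in the past tense, so these dates are facts to report and not choices still to be made. The pro forma has a field for the operation date, so an analyst can see when each visit fell due and which patients could have reached it. Stating the two dates when the results are reported would be good practice, but it alters neither the design nor the comparison. This conclusion would change only with evidence that follow-up in fact stopped at the end of August 2021 while patients operated on after February 2021 were still awaiting their 6-month visit.

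### The protocol states no random or concealed rule for assigning patients to closure or non-closure, and its cohort-with-CONSORT label does not settle the design

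*Protocol*

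**What the plan says.** Under ENROLLMENT OF PATIENTS the protocol first says that outpatients who met the inclusion criteria entered the study. It continues: "A total of 88 patients were enrolled in the study using the purposive alternate number sampling" technique. The next sentence is "They were divided into 2 groups: 44 patients each in the defect closure and non-closure groups". Nothing else in the document concerns how a patient reached an arm. It mentions no random sequence, list, envelope or concealment, and no person responsible for assignment.

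Under Materials and Methods, item a), the design is "A prospective cohort study reported as the CONSORT guideline". The alternate hypothesis is that closure is superior. The two primary objectives that depend on the comparison are "To compare Seroma formation rate in defect closure and non-closure groups" and "To compare the score of pain in VAS on different interval of time in both groups".

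**The concern.** How patients reach an arm is a core protocol item and is not normally left to the SAP. Here the one method named is ambiguous, and neither meaning protects the comparison. If whoever enrols patients can foresee or choose the arm, patients with a worse outlook for seroma or pain can end up more often on one side. A difference between arms could then reflect who was placed where, not the effect of closing the defect. Both primary outcomes and the superiority claim are exposed.

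The label adds to the difficulty. In a cohort study the groups arise from care as given, whereas here the text says that patients were divided into two equal groups. CONSORT is a reporting standard for randomised trials, and nothing in the text describes randomisation. A reader cannot tell from the label how strong a causal claim is intended.

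**Working it through.** **The plan's own figure.** 44 + 44 = 88, so the group sizes agree with the total.

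**What the equal split shows.** Under simple unrestricted 1:1 randomisation, the chance of exactly 44/44 is C(88,44)/2^88 = 0.085. Strict alternation of 88 patients gives 44/44 with certainty; filling to a quota or using a blocked random list gives it too. The split therefore does not identify the method.

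**The two readings of the named method.**
- It governs assignment: under strict alternation every arm after the first is known in advance.
- It governs enrolment, as the grammar suggests: the sentence on division then states no rule at all.

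Neither reading yields a random or concealed sequence.

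**What steering could do (all inputs assumed).** Take 44 per arm, no true effect of closure and a two-sided 5% test. Half of all patients are high-risk. A share w of one arm is high-risk, and 1 − w of the other. With seroma risks h (high) and l (low), the arm risks are

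p1 = w·h + (1 − w)·l and p2 = (1 − w)·h + w·l.

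For example, h = 40%, l = 10% and w = 0.7 give p1 = 0.28 + 0.03 = 31% and p2 = 0.12 + 0.07 = 19%. The false-positive rate is the exact sum, over two binomials with n = 44, of outcomes with pooled |z| > 1.96:

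| Risks h/l | No steering (50/50) | 60/40 | 70/30 |
|---|---|---|---|
| 20/10% | 5.5% | 6.3% | 8.7% |
| 30/10% | 5.4% | 8.0% | 16.1% |
| 40/10% | 5.3% | 10.4% | 26.3% |

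A 60/40 mix is about 26 against 18 high-risk patients (0.6 × 44 = 26.4; 0.4 × 44 = 17.6). A 70/30 mix is about 31 against 13. Fisher's exact test is more conservative: 2.5-2.7% without steering, 3.0-6.0% at 60/40 and 4.5-17.8% at 70/30.

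**VAS at one time point.** Let the two patient types differ by d SD. The arm means then differ by (2w − 1)·d; for example 0.4 × 0.8 = 0.32 SD at 70/30. Simulated t-tests (86 df, 200,000 runs each) for d = 0.3, 0.5 and 0.8 reject in 5.0%, 5.1% and 5.0% without steering, in 5.9%, 7.3% and 10.6% at 60/40, and in 8.6%, 14.8% and 28.8% at 70/30.

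**What adjustment can recover.** In the worst seroma case (26.3% unadjusted), a Mantel-Haenszel analysis (40,000 simulated runs) brings the rate to about 5% if the stratifying factor is what drove selection. It leaves 14.4% if the factor agrees with the driver in 80% of patients, 22.4% at 65% agreement and 25.2% if it is unrelated.

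**The case against.** The protocol never says that patients were randomised or that assignment was concealed, so it makes no false claim. The gap could be called one of description, deserving a lower priority. The first half of this stands: a reader might infer from the CONSORT reference that randomisation is asserted, but the text does not assert it. The priority is a different matter, because the missing rule bears on both primary outcomes and on the superiority hypothesis.

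The sentence before the quoted one can be read as enrolment by criteria alone, so the word purposive need not mean free choice over who enters. This also stands in part. It may limit discretion over entry, but not over which arm a patient receives.

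The steering figures rest on invented mixes and risks, the largest come from the most extreme cell, and alternation without steering does not inflate error. All of this is right. A reader might infer that the results are biased, or that roughly a quarter of null comparisons would come out positive. The documents support neither inference: no text shows that steering took place, and the equal split does not even show that alternation was used. The figures show only that bias is possible and how large it could be.

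Finally, defect size may be a poor adjustment factor. Eligibility requires at least M3, with "Defect size ≤M2" an exclusion, so a recorded grade may hardly vary, and the proforma field is to be completed only where applicable. That is accepted in the fix.

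**Conclusion.** The point holds as a defect in how group formation and design are described. On either reading of the named method, no random or concealed assignment is stated, and the cohort and CONSORT halves of the label conflict. The seroma and VAS comparisons are therefore open to selection bias, and the text as written supports a causal superiority conclusion only weakly.

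The size of any bias cannot be determined from the documents. Under the stated assumptions (half of patients high-risk, no true effect, 44 per arm, pooled z), the seroma false-positive rate is about 6-10% at a 60/40 mix and 9-26% at 70/30, against about 5% without steering. No sample-size or power figure changes. The point should be corrected before any superiority claim is made, because it reaches both primary outcomes and the core correction is cheap.

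**What to change.** 1. State how the arm was assigned, by whom, and when relative to consent.
2. Unless records show a random, concealed list:
   - Replace the design label with *prospective non-randomised comparative study*, adding *alternate assignment* only if that was the method.
   - Limit the superiority conclusion to association.
   - Report seroma and VAS also adjusted for one baseline factor, chosen before outcomes are examined and the same for both. Age or ASA grade would serve; defect size only if it is recorded for every patient and varies within M3 and above. Say that this removes only bias carried by that factor, and call the analysis post hoc if outcomes by arm have already been seen. The details may sit in the SAP.
3. If a random concealed list was used, describe it and drop the restrictions in item 2.

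Optional checks:
- If the proforma serial numbers follow enrolment order and the arm can be recovered for each patient, count the runs of arms. Strict alternation gives 88; a random order of 44 and 44 gives 2 × 44 × 44/88 + 1 = 45 on average, SD 4.7. This cannot reveal skipped patients.
- If a clinic register exists, which the protocol does not say, compare the 88 with the eligible outpatients of the study period.
- A concealed random list for later patients matters only if enrolment is still open. The protocol describes enrolment in the past tense and the study period as ending in August 2021.

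The cost is a weaker claim, a few reworded lines and one extra analysis per primary outcome. No new patients are needed.

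### Both primary outcomes depend on judgement, and the protocol masks neither the patients nor whoever records follow-up, so expectation can create or distort a difference between closure and non-closure.

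*Protocol*

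**What the plan says.** The Primary Objectives are "To compare Seroma formation rate in defect closure and non-closure groups" and "To compare the score of pain in VAS on different interval of time in both groups".

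- **Pain.** At discharge each patient receives a chart for daily self-assessment. The follow-up pages themselves hold only a yes/no entry for pain.
- **Seroma.** The follow-up form is described as a "seroma formation questionnaire to be filled up by 10 days, 30 days, 3 months and 6 months". Each visit has one yes/no entry, with no size threshold, imaging or diagnostic criterion. The person who completes it is not named.
- **Design and allocation.** The study is "A prospective cohort study reported as the CONSORT guideline". The Enrollment section says that 88 patients entered "using the purposive alternate number sampling" technique and were then divided into two groups of 44.
- **Forms.** The Annexures open with a proforma that begins "Particulars of patient Serial no" and includes a free-text line for the operative procedure. The follow-up form comes after it.
- **Direction.** The alternate hypothesis is one-directional: "Defect closure is superior to non-closure in laparoscopic direct inguinal hernia repair".

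Masking of patients, surgeons or follow-up assessors is not mentioned anywhere.

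**The concern.** An expectation can enter a primary result only if someone who knows the arm also has discretion over what is recorded. Here both primary outcomes leave that discretion, and nothing in the protocol withholds the arm. Someone who expects closure to work may read a borderline groin swelling differently in the two arms. A patient who knows whether the defect was closed may score pain with that in mind.

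This is not detail that a statistical analysis plan would normally supply. Who knows the arm, who assesses and what the assessor's sheet shows are matters of conduct. Once a visit has been recorded with the arm known, no analysis can separate expectation from effect. At stake is whether a significant difference on either primary outcome can be attributed to closing the defect.

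**Working it through.** The protocol states no significance level, power, expected rate or SD, so there is no figure of its own to reproduce. What follows shows how far assumed bias would move the false-positive rate.

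**Inputs from the protocol.** 44 patients per arm; a binary seroma outcome; a VAS outcome.

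**Assumptions.** Two-sided 5% test; no true difference; true seroma rate p = 20% in both arms; the sizes of bias shown below.

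**Seroma.** Let m be the share of closure-arm seromas not recorded, and f the share of seroma-free non-closure patients recorded as having one.

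- Recorded closure rate = p(1 − m)
- Recorded non-closure rate = p + (1 − p)f

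For m = 20% and f = 5%, these are 0.20 × 0.80 = 0.16 and 0.20 + 0.80 × 0.05 = 0.24. The probability of p ≤ 0.05 was found by enumerating every pair of counts from two binomials with n = 44.

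| Assumed bias (m, f) | Recorded: closure vs non-closure | Chi-square | Fisher |
|---|---|---|---|
| none | 20% vs 20% | 5.4% | 2.5% |
| 10%, 2.5% | 18% vs 22% | 8.0% | 4.1% |
| 20%, 0% | 16% vs 20% | 8.2% | 4.2% |
| 20%, 5% | 16% vs 24% | 16.1% | 9.6% |
| 20%, 10% | 16% vs 28% | 28.4% | 19.1% |

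In the 16% vs 24% case, 15.9 of the 16.1 percentage points are false findings in favour of closure. For that same bias (20%, 5%), true rates of 10% and 30% give 17.3% and 17.1% by chi-square, and 9.1% and 11.2% by Fisher. The result therefore depends little on the assumed true rate.

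**VAS at one time point.** For a shift of d standard deviations, the noncentrality is d√(n/2) = d√22, with 86 degrees of freedom.

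- d = 0.2: noncentrality 0.938, rejection probability 15.3%
- d = 0.3: noncentrality 1.407, rejection probability 28.5%

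These figures hold for a shift in either direction.

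**Routes to the arm.**

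1. The patient may be told, since nothing says otherwise.
2. The operative procedure is free text and may name closure.
3. If the alternating number is the proforma serial number, anyone who knows the rule can read the arm from it.

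The first needs no inference about the forms.

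**The case against.** **What stands.** Several stronger readings are tempting, and the protocol does not support them.

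- *The study is open-label.* It is silent on masking and does not declare this. What follows is that people can know the arm, not that they do.
- *One form displays the arm beside the outcome.* The follow-up form has its own title under the Annexures, and page breaks are not visible in the text at hand, so it may already be a separate sheet. The operative detail lists hernia type, contents and mesh, with no closure field.
- *The serial number is the arm.* The text does not say that the alternating number is the proforma serial number.
- *A clinician judges seroma.* No assessor is named.
- *Both biases favour closure.* A patient told of an extra closure step could expect more pain as readily as less.

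The sizes are also open to challenge. All the bias is assumed. Fisher's test is less affected, and the mildest case stays below 5% with it. The larger seroma figures need errors in both arms: missed seromas in the closure arm alone (16% vs 20%) give 8.2%, or 4.2% by Fisher.

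On cost, 88 patients with four scheduled visits make 352 assessments. The protocol gives no team size, so a non-operating assessor throughout cannot be called free. Parts of the protocol are in the past tense, with a study period ending in August 2021, so changes of conduct may come too late.

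**What does not remove the point.** Both outcomes still leave room for judgement, no masking is provided, and no later analysis can add it.

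**Conclusion.** The concern holds in limited form. The protocol leaves both primary outcomes open to expectation bias by masking neither patients nor follow-up assessment. For seroma, the stated hypothesis makes a bias towards closure the most plausible direction; for pain, the direction is uncertain.

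Under the assumed seroma biases acting in both arms, the false-positive rate rises from 5.4% to between 8% and 28% by chi-square, or from 2.5% to between 4% and 19% by Fisher. For VAS, a shift of 0.2 to 0.3 SD gives 15% to 29%. These are illustrations and not estimates: they rest on equal true rates of 20%, a two-sided 5% test and bias sizes on which the protocol gives no information.

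A reader might infer that the forms reveal every patient's arm, or that a positive result would be spurious. The protocol supports neither. It supports only that a difference on either outcome could not be cleanly separated from expectation.

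**What to change.** State in the protocol:

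1. Patients are not told their arm until the 6-month visit is complete, unless clinical care requires it. Both arms have the same laparoscopic approach, and the exclusion "Patient unfit for general anesthesia" implies general anaesthesia for all, so this looks practicable. It is the only one of the three changes that protects the patient's daily VAS chart.
2. Follow-up is recorded on a sheet separate from the operative pages, with a non-sequential ID that does not reveal allocation order.
3. Where existing staffing allows, the sheet is completed by a team member who did not operate on that patient, before the operation note is consulted, with an exception for complications.

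Masking does not replace a seroma criterion. Writing one down would further reduce the room for judgement.

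**Cost.** Consent wording, a split form and some rota swapping. The first two changes need no extra staff; the third depends on the team available.

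**If visits are already complete.** State who knew the arm at each assessment, and temper the superiority conclusion for both outcomes accordingly.
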